Briefly describe study design and anticipated enrollment, i.e., number of subjects to be enrolled by researchers study-wide and by Partners researchers. Provide a brief summary of the eligibility criteria (for example, age range, gender, medical condition). Include any local site restrictions, for example, “Enrollment at Partners will be limited to adults although the sponsor’s protocol is open to both children and adults.”

a. Overview

We will conduct a Stage 1 pilot feasibility study at McLean Hospital to develop a medication to treat nicotine dependence. (FIGURE 1) In a randomized, double-blind, placebo-controlled trial, 40 nicotine-dependent participants ages 18-65 will receive cognitive behavioral therapy (CBT) and nicotine replacement therapy (NRT) over a 10-week period, with half receiving D-cycloserine (DCS) pretreatment and half receiving placebo. Participants will receive either 250 mg DCS or placebo prior to weekly CBT sessions in addition to NRT over a 10-week treatment period. We also aim to determine the effects of DCS on performance on neuropsychological tests. A 10-week treatment period will be followed by follow-up assessments including neuropsychological tests at 1 and 3 months post-treatment. Primary outcomes will include smoking as measured by carbon monoxide levels and self-report measurements.

b. Source of subjects and recruitment methods

Forty participants ages 18-65 with DSM-IV diagnosis of nicotine dependence will be recruited from McLean Hospital outpatient programs and from the Boston area via newspaper advertisements, flyers, Craigslist online ads, clinician referrals, and word-of-mouth.

Briefly describe study procedures. Include any local site restrictions, for example, “Subjects enrolled at Partners will not participate in the pharmacokinetic portion of the study.” Describe study endpoints.

a. Recruitment and Intake

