Study participants will be randomized to receive either DCS or placebo and stratified according to baseline expired CO level (10-20 ppm and >20 ppm).

a.1. Availability and Flow of Subjects into Treatment

After approximately 240 telephone screens, we plan to conduct in-person screens of 40 individuals in the course of 18 months to achieve our desired sample size. Based our prior smoking-related studies, we estimate that there will be approximately 16 potentially eligible participants per month from treatment programs at McLean Hospital and the other Boston area recruitment methods and an adequate flow of participants to meet our target of 2.5 participants per month.

a.2. Study Visits and Participant Payments. Each weekly visit over 10 weeks will include a 50-minute CBT session and dispensing of pills. Research assessments will take place at 4 and 10 weeks of treatment and 4 and 12 weeks post-treatment. See Table D.1, Schedule of Measures. Participants will earn \$50 for the initial screen, \$20 for each of the 10 Actiwatch/Diary visits, a \$10 gift card for the completion of additional neuropsychological assessments at week 3, \$50 for each of the 4 Follow-Up Interviews, and a bonus \$50 for diary completion, for a total of \$510. Medication and therapy will be provided at no cost.

a.3. Clinical Emergencies. If a participant is intoxicated, the participant will be evaluated medically, sent home in a taxi when safe, and the appointment re-scheduled. If a participant experiences a problem that requires clinical

intervention during the course of the study (e.g., mania, suicidal ideation, or dangerous intoxication), we will evaluate the situation medically, make an appropriate recommendation, and help the participant to implement this plan. This could involve hospitalization at McLean, referral to the hospital's outpatient program, or other medical or psychiatric treatment, as clinically appropriate.

b. Drugs to be used

b.1. D-cycloserine. D-cycloserine (DCS)(Seromycin®, The Chao Center, West Lafayette, IN) is an FDA-approved broad spectrum antibiotic for the treatment of tuberculosis.

Participants will be randomized to receive either placebo or DCS 250 mg, given 1 hour prior to weekly CBT sessions. The McLean Research Pharmacy will randomize the participants and dispense medication or placebo weekly to the study physician, who

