d.2. Self-Report of Smoking. Participants will receive a packet of 1 page, self-addressed, prepaid postage Daily Diary pages. The diary consists of questions about smoking and other drug use as well as eating and sleeping habits. We have had excellent compliance with these diaries in the past. During the weekly visits, we plan to collect cigarette use data using the Timeline Follow Back (TLFB) (Sobell and Sobell, 1992) protocol.

d.3. Alveolar carbon monoxide (CO). End-expiratory CO will be measured after a 10-second breath-hold using a P.K. Morgan CO analyzer (Chatham, Kent, UK) at baseline, each CBT session, and each follow-up visit. Abstinence from cigarettes will be verified by an expired air CO concentration ≤ 10 ppm.

d.4. Other Assessments. We developed the self-administered Drug and Alcohol Use Questionnaire (Weiss et al. 1988), a baseline measure that addresses the context of lifetime and recent drug and alcohol use, as well as sociodemographic data. Function in multiple spheres of the participants' lives will be obtained at baseline and monthly using the LIFE functional assessment (Keller et al. 1987). HIV risk behaviors will be assessed at baseline and weeks 10, 14, and 22 with the Risk Assessment Battery (Metzger 1992). To assess treatment services outside the study that patients use, we will administer the Treatment Services Review (TSR) (McLellan et al. 1992) at baseline and monthly. The Client Satisfaction Questionnaire (CSQ-8) is an 8-item self-report scale will assess satisfaction with treatment. The Quick Inventory of Depressive Symptomatology (QIDS-SR) is a short self-report questionnaire for depressive symptoms used successfully in the STAR*D project. At baseline and week 3, several standard self-report questionnaires will be used to assess cigarette craving: Tiffany QUS Brief form, nicotine withdrawal: Wisconsin Smoking Withdrawal Scale, and affect: Positive and negative affect scales (PANAS). Menstrual cycle phase information also will be collected in women.

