d.5. Neuropsychological Assessment. (see Appendix for description of assessments) We will use a brief battery of standard, well-known neuropsychological tests designed primarily to evaluate general intellectual capacity and executive/attentional functions. All test scoring will be completed blind to participants' clinical ratings. The WASI 4-subtest version (Vocabulary, Similarities, Block Design and Matrix Reasoning) is a reliable, brief assessment used to obtain IQ estimates (Wechsler 1981). The Rey Auditory Verbal Learning Test (RAVLT) assesses immediate memory span, new learning, susceptibility to interference, and recognition memory (Lezak et al. 2004). The Stroop Color Word Task challenges the ability to inhibit inappropriate responses and resist interference (Bush et al. 2003). The Multi-Source Interference Task (MSIT) has been shown to reliably and robustly activate cingulo-frontal-parietal circuitry associated with cognitive/attentional pathways (Bush and Shin, 2006). The Go/No Go Task is a task of inhibitory control (Menon et al. 2001).

Table D.1 Schedule of Measures

Baseline only

Physical examination

Structured Clinical Interview for
DSM-IV

Menstrual Cycle Info. (Women only)

Drug and Alcohol Use Questionnaire

Wechsler Abbreviated Scale of Intelligence

Tiffany QUS Brief form

Wisconsin Smoking Withdrawal Scale

Positive and Negative Affect Scales (PANAS)

Baseline and week 3

Tiffany QUS Brief form

Wisconsin Smoking Withdrawal Scale

Positive and Negative Affect Scales (PANAS)

Menstrual Cycle Info. (Women Only)

Baseline, weeks 10, 14, and 22

ECG

Rey Auditory Verbal Learning Test

Multi-Source Interference Task

Assessment (from the LIFE)

Quick Inventory of Depressive Symptomatology

Client Satisfaction Questionnaire-8

Laboratory tests^a

Stroop Color Word Test

Timeline Followback Functional

Risk Assessment Battery

Fagerstrom Test for Nicotine

Dependence

^aTests include urinalysis, electrolytes, complete blood count, & blood chemistries

Baseline and weekly

Daily Diary

Alveolar Carbon Monoxide (CO)

Adverse Events & Side Effects

Baseline and monthly

LIFE

Treatment Services Review

Urine pregnancy test

8.2. Data Analysis.

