A relatively similar analytic approach will be used to assess the effect of DCS on changes in expired CO assessments. A linear mixed effects model will be used to assess changes in CO during treatment and at post-treatment follow-up. The linear mixed effects model will include the effects of treatment group, time and the baseline measure of CO; the inclusion of random effects accounts for the correlation among the 12 post-baseline CO measurements (1-per week during 10 weeks of treatment, plus week 14 and 22). We will adjust for the dose of NRT by including dose as an additional covariate in the linear mixed effects model analysis of the treatment comparison (DCS vs. placebo). The linear mixed effects model includes random intercepts and random slopes for time to appropriately account for correlation among repeated measures of CO and heterogeneity of variance over time; the model will be fit using PROC MIXED in SAS.

Analyses of secondary outcomes will focus on assessing the effect of DCS on neuropsychological assessments. For example, linear mixed effects models will also be used to analyze quantitative/continuous neuropsychological outcomes (e.g., MSIT response accuracy and times), with appropriate transformation (e.g., log transformation) of the outcome as necessary. To examine the effect of DCS on changes in neuropsychological performance during treatment, the linear mixed effects model will include the effects of treatment condition and the baseline measure of the neuropsychological outcome. Additional analyses of secondary outcomes will focus on the number of days of cigarette smoking during treatment and post-treatment follow-up. Frequency of days of cigarette use will be analyzed via a log-linear (or Poisson) regression model, controlling for pre-treatment frequency of days of cigarette use. Although log-linear regression methods are considered appropriate for the analysis of count or frequency data, in many biomedical applications, count data have variability that far exceeds that predicted by the Poisson distribution; we expect that days of cigarette use will not be an exception. This phenomenon, known as overdispersion, will be accounted for in the planned regression analysis through the inclusion of a

dispersion parameter. The log-linear regression analyses will be fit using PROC GENMOD in SAS.

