Proficiency in English is necessary for a long-term treatment study that includes 10 CBT sessions and ensures that the participants can properly convey any subtle side effects that relate to their safe participation in this study.

For guidance, refer to the following Partners policy:

Obtaining and Documenting Informed Consent of Subjects who do not Speak English

https://partnershealthcare-public.sharepoint.com/ClinicalResearch/Non-English_Speaking_Subjects.1.10.pdf

RECRUITMENT PROCEDURES

Explain in detail the specific methodology that will be used to recruit subjects. Specifically address how, when, where and by whom subjects will be identified and approached about participation. Include any specific recruitment methods used to enhance recruitment of women and minorities.

a. Inclusion Criteria. 1) Age range 18-65 years; 2) DSM-IV diagnosis of nicotine dependence, based on the Structured Clinical Interview for DSM-IV (SCID) (First et al. 1996); 3) express a desire to quit cigarette smoking within the next 30 days; 4) smokes greater than or equal to 10 cigarettes per day and less than or equal to 20 cigarettes per day; 5) an expired carbon monoxide (CO) determination greater than or equal to 10 ppm over ambient values; 6) for women of childbearing age, a negative pregnancy test at screening with agreement to use adequate contraception to prevent pregnancy and multiple subsequent pregnancy tests; 7) consent for us to communicate with their prescribing clinician; 8) furnish the names of 2 locators, who would assist study staff in locating them during the study period; 9) live close enough to McLean Hospital to attend study visits; 10) plan to remain in the Boston area for the next 4 months; and 11) are willing and able to sign informed consent.

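### Inclusion item 10 asks for a planned stay of 4 months (about 17.4 weeks), but the last visit is at week 22 (5.06 months), so people who already plan to leave before the only 3-month post-treatment assessment can be enrolled

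*Combined protocol and SAP*

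**What the plan says.** Recruitment Procedures, Inclusion Criteria, item 10 requires that candidates "plan to remain in the Boston area for the next 4 months". It is the only criterion that states how long a person must expect to stay. Item 9 asks that they "live close enough to McLean Hospital to attend study visits", with no duration, and item 8 asks for two contacts who can help staff find them.

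The schedule runs longer than 4 months, and several sections agree on its end:

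- The Overview plans "follow-up assessments including neuropsychological tests at 1 and 3 months post-treatment".
- Section a.2 states: "Research assessments will take place at 4 and 10 weeks of treatment and 4 and 12 weeks post-treatment".
- Table D.1 has a block of measures at "Baseline, weeks 10, 14, and 22".
- Section 8.2 counts the post-baseline CO values as "1-per week during 10 weeks of treatment, plus week 14 and 22".
- Section d.3 measures CO "at baseline, each CBT session, and each follow-up visit".

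**The concern.** An eligibility rule about planned residence exists to secure attendance for the whole study. This one covers treatment and the week-14 visit but ends before week 22. A candidate who says at screening that they will leave Boston between month 4 and week 22 satisfies item 10 as written.

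Week 22 is the only look at smoking and neuropsychological performance 3 months after treatment. Most of what is done there needs the person present: expired CO on the analyzer, RAVLT, Stroop, MSIT, ECG and laboratory tests. Section d.3 verifies abstinence by expired CO, and the protocol describes no remote substitute, so someone who has moved away could at best report smoking status without verification. At stake is missing data that can be foreseen at screening, at the one visit that describes durability, with 20 people per arm.

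**Working it through.** **Inputs.** Required stay: 4 months (item 10). Treatment: 10 weeks; follow-up: 4 and 12 weeks post-treatment (section a.2). Randomized: 40, 20 per arm; within-participant correlation 0.3 to 0.7 (section 8.2 c). Conversion: 365.25/12/7 = 4.348 weeks per month.

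**The plan's own figures.** 10 + 4 = week 14 and 10 + 12 = week 22, as in Table D.1. Ten weekly values plus two at follow-up give 12 post-baseline CO values, as in section 8.2 a. Both reproduce.

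**The gap.** 4 × 4.348 = 17.4 weeks (about 122 days). Week 22 = 22 × 7 = 154 days = 22/4.348 = 5.06 months. Shortfall: 22 − 17.4 = 4.6 weeks, about 32 days. Week 14 = 14/4.348 = 3.22 months, so it is covered.

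Other readings do not close the gap:

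| Reading | Required stay (weeks) | Last visit (week) | Shortfall (weeks) |
|---|---|---|---|
| Average months | 17.4 | 22 | 4.6 |
| Longest four calendar months (123 days) | 17.6 | 22 | 4.4 |
| 4-week months | 16 | 22 | 6.0 |
| Follow-up at 3 calendar months (10 + 3 × 4.348) | 17.4 | 23.04 | 5.7 |

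If the 4 months run from screening, the interval from screening to the start of treatment, which the protocol does not give, adds to each shortfall.

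**Consequence, per person lost at week 22.** 1/20 = 5% of that arm's week-22 data; 1 of that person's 12 CO values; 1 of the 3 post-baseline RAVLT, Stroop and MSIT assessments in Table D.1.

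**Consequence, for the trial.** The number of planned leavers is not in the documents. I assume 0 to 4 of 40.

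- Week-22 data: 0/40 to 4/40 = 0 to 10%.
- CO values: 40 × 12 = 480; 0/480 to 4/480 = 0 to 0.83%.
- Abstinence (GEE): with exchangeable correlation ρ and m repeats, information per person is m/(1 + (m − 1)ρ). The protocol does not state m. Table D.1 lists Timeline Followback at three post-baseline visits (m = 3); section d.2 collects it at weekly visits, which with the two follow-ups gives m = 12.

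| m | ρ | Information, all visits | Without week 22 | Loss per leaver | Loss overall, 4 of 40 |
|---|---|---|---|---|---|
| 3 | 0.3 | 1.875 | 1.538 | 17.9% | 1.8% |
| 3 | 0.5 | 1.500 | 1.333 | 11.1% | 1.1% |
| 3 | 0.7 | 1.250 | 1.176 | 5.9% | 0.6% |
| 12 | 0.3 | 2.791 | 2.750 | 1.46% | 0.15% |
| 12 | 0.5 | 1.846 | 1.833 | 0.69% | 0.07% |
| 12 | 0.7 | 1.379 | 1.375 | 0.31% | 0.03% |

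The overall loss is the per-leaver loss times 4/40, and is zero if nobody plans to leave.

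**The case against.** The strongest reply is that no harm is demonstrated. The number of planned leavers may be zero, the 0 to 4 range is an assumption, and the effect on the primary tests is small even at its upper end. The 1.8% needs 4 leavers, ρ = 0.3 and only three abstinence repeats; weekly Timeline Followback points to the 12-repeat case, where the maximum is 0.15%. All of this stands, and it limits the importance of the point.

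The analysis plan also specifies no week-22 contrast. The abstinence model has no time term. The CO model has a time effect but no stated comparison at week 22. The neuropsychological model described in section 8.2 concerns change during treatment. So what suffers is description, in a pilot that calls itself exploratory. That is right, but the protocol schedules the 3-month visit and puts its CO value into a primary model, so the visit is meant to yield data.

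Item 9 could be applied to someone who announces a move, since week 22 is a study visit. Some staff might do so, but item 9 gives no time horizon while item 10 gives an explicit one that is too short. The locators, the $50 paid for each follow-up interview, the commitment to keep assessing people who stop treatment, and the missing-data sensitivity analyses all help. None requires a planned stay to week 22, and no analysis recovers a visit that did not take place.

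**Conclusion.** The mismatch is certain: the required stay ends about 4.6 weeks before the last visit, and at least 4.4 weeks before it under every reading of a month tried. Its effect is uncertain and may be nil, because the rate of planned departure is unknown. Each loss costs 5% of an arm at week 22. Under the assumed 0 to 4 leavers, 0 to 10% of week-22 data are missing, with at most 0.83% of CO values and at most 1.8% of abstinence information lost. The information figures assume exchangeable correlation in the protocol's range of 0.3 to 0.7. No bias between arms is shown, since a plan to move held at screening precedes randomization. The power statement does not use this criterion. The correction should be made because it is almost free, although the expected damage is small.

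**What to change.** Reword item 10 to require a plan to remain in the Boston area through the week-22 follow-up visit. Tying it to the visit is safer than a round number of months: 5 months is 21.74 weeks, just short of week 22 even with no screening delay. If a duration is preferred, about 6 months from screening (26.1 weeks) leaves 26.1 − 22 = 4.1 weeks for that delay, but it could exclude a few people who would be able to complete every visit.

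The cost is a one-line amendment and a matching line in the telephone screen. Treatment, sample size and analysis are unchanged. Eligibility narrows slightly. Section a.1 expects "approximately 16 potentially eligible participants per month" against a target of 2.5, which suggests room. That figure should not be leaned on heavily: 16 × 18 months = 288, more than the roughly 240 telephone screens planned in the same section (240/18 = 13.3 per month). Asking the question at the telephone screen keeps the cost low, because only 40 in-person screens are planned.

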Provide a brief description of any foreseeable risks and discomforts to subjects. Include those related to drugs/devices/procedures being studied and/or administered/performed solely for research purposes. In addition, include psychosocial risks, and risks related to privacy and confidentiality. When applicable, describe risks to a developing fetus or nursing infant.

a. Drug side effects and toxicities

D-cycloserine has been shown to have a favorable safety profile in studies; it has been well-tolerated in several clinical trials and no adverse events have been reported in these studies (Santa Ana et al. 2009; Storch et al. 2010; Evans and Drobos, 2008; Goff et al. 2008). Most adverse reactions occurring during therapy with D-cycloserine involve the nervous system or are manifestations of drug hypersensitivity (Seromycin package insert). Nervous system side effects appear to be related to higher doses (500 mg daily or above) and include drowsiness, headache, tremor, psychoses, and hyperirritability. Sudden development of congestive heart failure has been reported in patients receiving 1 to 1.5 g of D-cycloserine daily. Nicotine can cause headache and skin irritation.

b. Psychosocial risks

There is a low likelihood that participants previously screened for significant psychiatric disorders will be triggered by content of therapy sessions. As mood may be affected, we will monitor mood and suicidal ideation weekly with the Columbia Suicide Severity Scale.

EXPECTED BENEFITS

Describe both the expected benefits to individual subjects participating in the research and the importance of the knowledge that may reasonably be expected to result from the study. Provide a brief, realistic summary of potential benefits to subjects, for example, “It is hoped that the treatment will result in a partial reduction in tumor size in at least 25% of the enrolled subjects.” Indicate how the results of the study will benefit future patients with the disease/condition being studied and/or society, e.g., through increased knowledge of human physiology or behavior, improved safety, or technological advances.

a. Potential benefits to participating individuals

Participants may be able to stop or reduce their smoking, which would have enormous health and financial benefit to them.

b. Potential benefit to society

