NOTE: In addition to the adverse event reporting requirements of the sponsor, the principal investigator must follow the Partners Human Research Committee guidelines for Adverse Event Reporting

The Principal Investigator assumes responsibility for ensuring informed consent, data management, and the detection and reporting of adverse events. In general, the data to be reviewed will include screening data, baseline data, efficacy data, safety data, quality assurance data, accrual status including projections, and any other data that will help in the assessment of the effectiveness of the clinical trial.

The risk associated with participating in this study is moderate. D-cycloserine has been established as a safe treatment for tuberculosis. Consequently, serious side effects associated with this treatment are not expected. There will be on-call medical coverage to respond to any adverse events throughout the clinical trial.

The Principal Investigator will conduct a review of all adverse events and determine the attribution and grade of severity of the adverse event by using the following scales:

Attribution of Risk Categories:

Definite: Adverse event(s) will clearly be related to investigational agent(s) or other intervention

Probable: Adverse event(s) will likely be related to investigational agent(s)

Possible: Adverse event(s) may be related to investigational agent(s)

Unlikely: Adverse event(s) will doubtfully be related to investigational agent(s)

Unrelated: Adverse event(s) will clearly not be related to the investigational agents(s)

Grades of Risk:

0: No adverse event or within normal limits

1: Mild adverse event

2: Moderate adverse event

3: Severe adverse event resulting in hospitalization or prolongation of existing hospitalization, a persistent or significant disability/incapacity, or a congenital anomaly/birth defect

4: Life-threatening or disabling adverse event

5: Fatal adverse event

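### The adverse-event severity scale has no grade for a severe but non-serious event and two for a disabling one, and the attribution categories do not share one referent

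*Combined protocol and SAP*

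**What the plan says.** In the combined protocol and SAP, Data and Safety Monitoring, the principal investigator reviews all adverse events and is to "determine the attribution and grade of severity of the adverse event by using the following scales". Two scales follow.

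- **Grades of Risk.** Grades 1 and 2 are defined by intensity only; grade 2 is simply "Moderate adverse event". Grade 3 is "Severe adverse event resulting in hospitalization or prolongation of existing hospitalization, a persistent or significant disability/incapacity", or a birth defect. The next grade reads "4: Life-threatening or disabling adverse event". Grade 5 is fatal.
- **Attribution of Risk Categories.** The top category is "Definite: Adverse event(s) will clearly be related to investigational agent(s) or other intervention". The bottom one is "Unrelated: Adverse event(s) will clearly not be related to the investigational agents(s)". *Probable*, *Possible* and *Unlikely* also refer to the investigational agent alone. The term is not defined.

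The same section then defines serious adverse events (SAEs). That list includes hospitalization or its prolongation, disability or incapacity, and congenital anomaly, which are the outcomes attached to grade 3. It also commits the investigator to review the frequency and severity of adverse events at least semi-annually and to decide whether the protocol or consent form should change.

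The randomized comparison is DCS against placebo, with CBT and nicotine patches in both arms (Specific Aims). Patch side effects go onto adverse event forms (Drugs to be used, b.2), and such effects are expected: "Nicotine can cause headache and skin irritation" (Foreseeable Risks and Discomforts; repeated under Safety Monitoring).

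**The concern.** A severity grade should place every event in exactly one category according to how intense it was. Whether it led to admission, disability or a birth defect is a separate question, that of seriousness. Here grade 3 asks both questions at once. An event that is severe but has no SAE outcome then seems to have nowhere to go, and disability is named in two adjacent grades.

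The attribution scale has a similar fault. Its five categories should be five degrees of the same relationship, but the top one covers a wider set of causes than the rest.

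What is at stake is the reliability of the coded safety data. The semi-annual review considers severity, and these are the only grading and attribution scales described for the investigator's assessment. No independent board or adjudicator is described who would resolve inconsistent codes. The study is also a pilot meant to inform a larger trial, so its tolerability tables should be interpretable.

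**Working it through.** The plan gives no figure to reproduce. The check is to read the definitions as logical rules and see what they assign.

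**Severity: inputs.** Take an event of severe intensity and five yes/no facts: hospitalization (H), disability or incapacity (D), congenital anomaly (C), life-threatening (L), fatal (F). From Grades of Risk:

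- grade 3 applies if H or D or C;
- grade 4 applies if L or D;
- grade 5 applies if F.

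Grades 1 and 2 are not available, because the event is neither mild nor moderate.

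**Gap.** There are 2^5 = 32 combinations. An event has no grade only if grade 3 fails (H = D = C = 0), grade 4 fails (L = D = 0) and grade 5 fails (F = 0). That is exactly 1 of 32: the severe event with none of the listed outcomes. This counts definitions and says nothing about how often such events occur. It is, however, the ordinary severe non-serious event, which can readily arise in an outpatient trial.

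**Overlap.** Of the 2^4 = 16 non-fatal combinations, D is present in 2^3 = 8, and all 8 meet both grade 3 and grade 4.

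The four combinations with H = L = F = 0 show both faults:

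| Disability | Birth defect | Grade(s) met |
|---|---|---|
| no | no | none |
| no | yes | 3 |
| yes | no | 3 and 4 |
| yes | yes | 3 and 4 |

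A rule to take the highest grade would settle the overlap, but the plan states none. Under such a rule the disability clause in grade 3 would never be used, unless disabling in grade 4 means something different, which is not explained. The rule would not fill the gap.

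**Attribution.** The result depends on what counts as an investigational agent, so both readings are shown.

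| Event | Agent = DCS/placebo only | Agent includes the patch |
|---|---|---|
| Clearly caused by the patch | *Definite* (as other intervention) and *Unrelated* | *Definite* only |
| Probably caused by the patch | no related category | *Probable* |
| Clearly caused by CBT | *Definite* and *Unrelated* | *Definite* and *Unrelated* |

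The first reading follows the randomized comparison. The second is possible: the term is written with an optional plural, and DCS and nicotine replacement both appear under Drugs to be used. Under either reading, an event clearly caused by CBT (taken as an other intervention) still receives two opposite labels.

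**The case against.** The strongest reply is that little in the plan turns on these codes, and much of it stands.

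- **Actions do not depend on grade.** The 48-hour report to the IRB follows the separate SAE definition and whether the event was unanticipated. Medication is discontinued for a clinically significant abnormality or for side effects that preclude continuing, and participation ends on the investigator's judgment. A disabling event is an SAE whether it is graded 3 or 4.
- **Intensity is collected elsewhere.** Safety Monitoring describes an adverse events checklist and a questionnaire on the frequency, intensity and burden of side effects, and Table D.1 schedules adverse events and side effects at baseline and weekly. This softens the gap. It does not close it, because the plan gives no mapping from those instruments to the investigator's grade.
- **The patch may be an investigational agent.** If so, the patch conflict disappears. The point therefore has to be conditional, and the missing definition is itself part of the fault.

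Three stronger readings are tempting, and the documents do not support them.

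1. A reader might infer that any severe event managed without admission is ungraded. It is not: with disability or a birth defect it is grade 3, if life-threatening grade 4, if fatal grade 5.
2. A reader might infer that, since all 40 participants are to use patches, nicotine reactions coded *Definite* would dilute a DCS safety signal. Section 8.2 plans no analysis by attribution category, patches are given in both randomized arms so that total counts can still be compared, and no event frequencies are given.
3. A reader might take the nervous-system effects listed under Foreseeable Risks and Discomforts as likely ungraded severe events. That text links them to 500 mg daily or above; this trial gives 250 mg once weekly.

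**Conclusion.** The severity scale is faulty as written. One class of severe event, with none of the listed outcomes, has no correct grade and would be pushed down to moderate or left blank. A severe disabling event has two grades with no rule to choose between them. This rests on the wording alone and needs no assumption about event rates.

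The attribution scale is inconsistent, because *Definite* has a wider referent than the other four categories. The particular conflict over patch reactions holds only if DCS/placebo is the sole investigational agent, which is the natural reading but is not stated.

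The impact is modest. It bears on the consistency of severity and attribution coding and on the semi-annual review. It does not bear on 48-hour IRB reporting or the discontinuation rules, and no loss of a DCS signal is shown. The change is still worth making, because the scales are stated rules that would miscode events and correcting them costs little.

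**What to change.** Under Data and Safety Monitoring:

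1. Grade severity by intensity alone: mild, moderate, severe, life-threatening, fatal. Remove the hospitalization, disability and birth-defect wording from grade 3 and the word disabling from grade 4.
2. Record seriousness as a separate yes/no item, using the SAE definition already in that section. Life-threatening and fatal events will still be serious by definition, which is harmless because each event then has one grade and one seriousness answer.
3. Define the investigational agent, saying whether it includes the nicotine patch, and use the same referent in all five attribution categories.
4. Optionally, add a second attribution field for the patch or other intervention. This is useful mainly if the agent is defined as DCS/placebo only, since patch reactions would then otherwise be coded only as unrelated to it. It is not needed to make the scale consistent.

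The cost is protocol wording and one or two fields on the adverse-event form, with no extra visits or staff.
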